5.3. Multicentre Studies

In this cluster-randomization design, each study centre, considered as a cluster, will be randomized to either ACT guided treatment group or control group (usual care group). The randomization will be stratified according to the hospital level (Tier 3 vs. Tier 2). The hospital level is determined in accordance with the uniform requirements of the government. A Tier 3 hospital is on a larger scale and provides superior medical care than a Tier 2 hospital. Centre, as the unit of randomization, will be treated as a random effect in generalized linear mixed model (GLMM) used to analyse primary endpoints.

5.4. Examination of Covariates, Other Strata and Subgroups

The primary endpoints will be analysed using mixed effect logistic regression. In this study, generalized linear mixed model (GLMM) will be used to control for centre as a random effect since each centre is considered as a cluster in this cluster-randomization study. The statistical model on which the inference will be based will include terms for treatment, baseline ACT total score, baseline ACT total score squared, centre, type of baseline controller (inhaled corticosteroids [ICS] alone vs. ICS/long-acting β 2 agonist [LABA]), gender and age. The primary endpoints will also be presented in the following subgroups: type of baseline controller (inhaled corticosteroids [ICS] alone vs. ICS/long-acting β 2 agonist [LABA]), gender and age (<50 years old vs. \geq 50 years old).

5.5. Multiple Comparisons and Multiplicity

The primary comparison of interest is the comparison between ACT and usual care for the primary endpoint in the ITT population. Analyses of efficacy endpoints will not be subject to any multiplicity adjustment.

5.6. Other Considerations for Data Analyses and Data Handling Conventions

Other considerations for data analyses and data handling conventions are outlined in the appendices:

Section	Component
10.3	Appendix 3: Study Phases and Treatment Emergent Adverse Events
10.4	Appendix 4: Derived and Transformed Data
10.5	Appendix 5: Reporting Standards for Missing Data
10.6	Appendix 6: Values of Potential Clinical Importance

6. STUDY POPULATION ANALYSES

6.1. Overview of Planned Study Population Analyses

The study population analyses will be based on the ITT population, unless otherwise specified.

Study population analyses including analyses of subject's disposition, population, protocol deviations, demographic and baseline characteristics, subject's smoking history, alcoholism history, drug abuse history, asthma history, asthma exacerbation history, medical history (coded by MedDRA version 21.0 or above), asthma medications, and concomitant medications (coded by WHODrug version Global Mar 2018 or above), will be summarized and listed. Details of the planned displays are presented in [Appendix 8: List of Data Displays](#).

7. EFFICACY ANALYSES

All hypothesis tests and confidence intervals will be two-sided. All efficacy measures over the course of the study will be presented and summarised. Continuous data will be summarised by means, standard deviations (SD), medians, minimum and maximum; categorical data will be summarised by counts and percentages.

All outcomes will be pertained to the individual participant's level and the analysis model will be adjusted for the effect of centre (cluster).

Unless otherwise specified, endpoints / variables defined in Section [7.1](#) and Section [7.2](#) will be summarised using descriptive statistics, graphically presented (where appropriate) and listed.

7.1. Primary Efficacy Analyses

7.1.1. Endpoint / Variables

The ACT is a validated self-administered questionnaire utilising 5 questions to assess asthma control during the past 4 weeks on a 5-point categorical scale (1 to 5).

The total score is calculated as the sum of the scores from all 5 questions, provided all scores are non-missing; if any individual scores are missing then the overall score will be set to missing.

The primary endpoint for the study is the percentage of subjects who have an ACT total score ≥ 20 or an improvement of more than 3 points in ACT total score in at least one post-baseline assessment during the 24-week treatment period.

The calculation of percentage will base on the subjects with at least one post-baseline ACT assessment.

7.1.2. Primary Analysis Methods

The primary endpoints will be analysed using mixed effect logistic regression. In this study, generalized linear mixed model (GLMM) will be used to control for centre as a random effect since each centre is considered as a cluster in this cluster-randomization study. The statistical model on which the inference will be based will include terms for treatment, baseline ACT total score, baseline ACT total score squared, centre, type of baseline controller (ICS alone vs. ICS/LABA), gender and age. Centre, as the unit of randomization, will be treated as a random effect. Type of baseline controller (ICS alone vs. ICS/LABA) derives from the current asthma medication record in visit 0. The results of the primary analyses will be presented as adjusted odds ratios, 2-sided 95% confidence intervals, and associated p-values comparing ACT guided treatment with usual care. The adjusted odds ratios and 95% confidence intervals will be presented by a forest plot.

The example SAS codes are as below:

```
proc glimmix data=input_data method=quad;
class invsite rndgrp blcontrol gender;
model response= rndgrp actbl actblsq blcontrol gender age /s
dist=binomial oddsratio cl link=logit;
random intercept/subject= invsite;
lsmeans rndgrp /diff cl;
run;
```

where `input_data` is the name of the input dataset and `response` is the response variable. In terms of the covariates `rndgrp`, `actbl`, `actblsq`, `blcontrol`, `gender` and `age` are variables for randomised treatment code, baseline ACT total score, baseline ACT total score squared, type of baseline controller, gender and age respectively. For random effect, `invsite` is variable for centre.

Interactions between treatment and each of the covariates will be investigated in turn, with all main effects in the model regardless of their statistical significance. Any interaction terms found to be statistically significant will be explored and if necessary results will be reported for each level of the covariate. Investigation of interactions will be confined to the primary endpoints. The effect of interactions (e.g., treatment by centre) will be assessed at the 10% level of significance.

Analyses of the primary endpoints will be performed on the ITT population and the PP population; the ITT population is considered primary. The PP population will not be analysed if this population comprises more than 95% or less than 50% of the ITT population. Only the primary efficacy variables will be analysed using the PP population.

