9.4. Key Elements of Analysis Plan

All hypothesis tests and confidence intervals will be two-sided. Except where otherwise stated, the estimation of treatment effect will be adjusted for the effects of centre, type of baseline controller (ICS alone vs. ICS/LABA), gender, and age. Centre, as the unit of randomization, will be treated as a random effect.

All efficacy measures over the course of the study will be presented and summarised in graphs and tables. Continuous data will be summarised by means, standard deviations, medians, minimum and maximum; categorical data will be summarised by counts and percentages.

All outcomes will be pertained to the individual participant's level and the analysis model will be adjusted for the effect of centre (cluster).

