9.4.1. Primary Analyses

The primary endpoints will be analyzed using logistic regression. The statistical model on which the inference will be based will include terms for treatment, centre, type of baseline controller (ICS alone vs. ICS/LABA), gender and age. Centre, as the unit of randomization, will be treated as a random effect. The results of the primary analyses will be presented as point estimates, 95% confidence intervals and associated p-values for the adjusted mean differences between ACT guided treatment and usual care.

Analyses of the primary endpoints will be performed on the ITT population and the PP population; the ITT population is considered primary.

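### The primary GLMM omits hospital Tier, the randomisation stratum, and states no between-centre degrees of freedom although treatment varies only between 12 centres; the stated 80% power holds only on a normal reference.

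*SAP*

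**What the plan says.** SAP 5.3: "The randomization will be stratified according to the hospital level (Tier 3 vs. Tier 2"). The same section says "A Tier 3 hospital is on a larger scale and provides superior medical care than a Tier 2 hospital".

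SAP 5.4 and 7.1.2 list the fixed effects of the primary model as treatment, baseline ACT and its square, baseline controller, gender and age, with centre random. SAP 7.1.2 says that the model "will include terms for treatment, baseline ACT total score, baseline ACT total score squared, centre, type of baseline controller", gender and age. SAP 5.4 reads "baseline ACT total score squared, centre, type of baseline controller (inhaled corticosteroids [ICS] alone" and so on. The example code agrees: "proc glimmix data=input_data method=quad" with "model response= rndgrp actbl actblsq blcontrol gender age /s" and a random intercept by centre. Tier is in neither the CLASS nor the MODEL statement. Protocol 9.4.1 has no Tier term either: "The statistical model on which the inference will be based will include terms for treatment, centre, type of baseline controller", gender and age. Protocol 9.4 has the same list: "the estimation of treatment effect will be adjusted for the effects of centre, type of baseline controller". Tier is not a subgroup or sensitivity factor in SAP 7.1.3.

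For inference, SAP 7.1.2 promises odds ratios, 95% intervals and p-values, without naming a reference distribution. The code has no degrees-of-freedom option. The linear mixed models in SAP 7.1.3 and 7.2.2 do set ddfm=kr.

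Protocol 9.2.1 plans 6 centres per arm, at least 35 evaluable subjects per centre (44 recruited), rates of 29% and 44%, ICC 0.01, two-sided alpha 0.05 and 80% power. It does not say whether the ICC is within Tier or total.

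**The concern.** The treatment contrast rests on 12 randomised units, however many patients each contributes. Two things about the primary test are left open, and they act in opposite directions.

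- **Reference distribution.** A normal or patient-level df reference treats the between-centre variance as better known than 12 centres allow. That can make the test liberal.
- **Tier.** If Tier predicts response and is balanced between arms, leaving it out puts its variance into the centre term. The test becomes conservative and loses power.

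There is no reason for the two to cancel. The true size of a nominal 5% primary test then depends on a Tier effect and an ICC that the documents do not settle. The planned power may also describe a more favourable test than a between-centre analysis can deliver.

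**Working it through.** **1. The plan's own power (inputs from Protocol 9.2.1).**
- Design effect: 1 + (35 − 1) × 0.01 = 1.34.
- Subjects per arm: 6 × 35 = 210.
- SE = √[(0.29 × 0.71 + 0.44 × 0.56) × 1.34 / 210] = √(0.4523 × 1.34 / 210) = 0.0537.
- Noncentrality: 0.15 / 0.0537 = 2.79.
- Normal reference: Φ(2.79 − 1.96) = 79.7%, which is the stated 80%.

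**2. The same inputs on between-centre df (noncentral t).**
- 10 df (12 − 2), critical value 2.228: 71.1%.
- 9 df (12 − 2 − 1 for Tier), critical value 2.262: 70.1%.
- If all 44 per centre are evaluable: design effect 1 + 43 × 0.01 = 1.43, noncentrality 3.03, 76.9% on 9 df.

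**3. Size and power by simulation.** There are 12 centres of 35 with beta-binomial responses. The null rate is 36.5%, the alternative 29% against 44%. Logistic random-intercept models were fitted by maximum likelihood with 21-node quadrature, 10,000 runs per cell. Assumptions not in the documents: 3 + 3 centres per Tier per arm, the Tier gap, and any ICC other than 0.01. Patient covariates are left out.

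Total ICC = w(1 − b) + b, with w the within-Tier ICC and b = (gap/2)² / (0.365 × 0.635). At a 15-point gap b = 0.005625 / 0.2318 = 0.024, so w = 0.01 gives a total of 0.034. At 10 points the total is 0.021.

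Within-Tier ICC 0.01:

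| Test | Size at gap 0 / 10 / 15 | Power at gap 0 / 10 / 15 |
|---|---|---|
| As written, normal | 6.9 / 4.7 / 2.9% | 81 / 75 / 65% |
| No Tier, t(10) | 3.9 / 2.6 / 1.5% | 73 / 65 / 53% |
| Tier, normal | 7.6 / 7.1 / 7.0% | not shown |
| Tier, t(9) | 4.0 / 3.9 / 3.5% | 74 / 74 / 75% |

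A Tier-adjusted centre-level t test on 9 df has size 4.7–5.2% and power 69–71% in this setting.

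Other settings:
- *ICC 0.05, no gap:* as written on a normal reference, 9.4%. A second simulation with logit-normal centres (1,500 runs per cell) gave 10.3%.
- *Within-Tier ICC 0.03–0.05:* Tier on t(9) has size 6.1–7.1%; the centre-level t(9) test has 4.7–5.3%.
- *Total ICC held at 0.01:* b = 0.01 caps the gap at 2 × √(0.01 × 0.2318) = 9.6 points. Power as written on a normal reference is 81/81/83/84% at gaps 0/5/8/9.6, against 74/76/79/82% for Tier on t(9).
- *Patient covariates added (assumed effects, 2,000 runs), within-Tier ICC 0.01, gaps 0/10/15:* as written on a normal reference, size is 6.4/5.4/3.0% and power 82/76/67%. Tier on t(9) gives size 3.8/4.5/4.0% and power 76/77/77%.

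**4. Interval width, Tier on t(9) against the written model on a normal reference.** Ratio = (2.262 / 1.960) × √[1.34 / (1 + 34 × total ICC)].
- No Tier effect: 1.154.
- 10 points: 1.154 × √(1.34 / 1.70) = 1.02.
- 15 points: 1.154 × √(1.34 / 2.16) = 0.91.

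**The case against.** **The random centre intercept already adjusts for centre.** It models the clustering, and that part stands. It does not fix the reference distribution, and it carries any Tier difference as noise instead of removing it.

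**A reader might infer that the primary test is anti-conservative as written.** The documents do not support that. They do not say which reference applies, and on t(10) the same model has size of about 4% at ICC 0.01. The 9–10% figure also needs an ICC five times the planned one. What the documents show is that the df are unstated.

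**A reader might infer that omitting Tier biases the treatment effect.** It does not when Tier is balanced by the stratified randomisation; the loss is in efficiency. The remark about superior care describes a hospital grade and gives no size for a difference in ACT response. If the ICC of 0.01 is the total, the written test on a normal reference loses no power, and the corrected test has lower power than it at every gap, partly because its size is lower. The net power gain is therefore undetermined.

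**The 70% is a low figure for the planned trial.** This stands in part. Protocol 9.2.1 calls 35 a minimum, and SAP 7.1.1 keeps anyone with one post-baseline ACT. The figure is 77% if all 44 are evaluable, and about 74% by simulation for the GLMM on t(9) at 35.

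**GLMM on t(9) does not hold size exactly.** True: it is slightly conservative at ICC 0.01 and mildly liberal at 0.03–0.05. That is the reason for the centre-level check.

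**Conclusion.** The point holds in a conditional form. Two facts need no assumption: the stratification factor is missing from the primary model, and the df for a comparison of 12 centres are unstated. The planned 80% also depends on a normal reference.

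The consequences are conditional:
- On a normal or residual-df reference, size is about 7% at ICC 0.01 with no Tier effect. With a balanced 15-point gap over a within-Tier ICC of 0.01 it is about 3%, with power of about 65%.
- On t(10) the test is not liberal at ICC 0.01, but power is already below plan.
- Tier with t(9) gives size of about 4% and power of about 74% across the gaps examined at within-Tier ICC 0.01.

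The Tier split, Tier effect and df default are assumptions. With uneven splits (5 + 7 or 3 + 9 centres) and gaps of 10–15 points, the written test on a normal reference has size 4.5–6.0%, so it is then not clearly conservative. The change should be made. Stating the df and restating the power is the firmer half; adding Tier is sound practice whose power gain cannot be known in advance.

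**What to change.** Make the first two edits together: df without Tier loses power if Tier matters (53% at 15 points), and Tier on a normal reference stays liberal (about 7%) at within-Tier ICC 0.01.

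1. **Tier.** Add it as a fixed effect in SAP 5.4 and 7.1.2 (text, CLASS and MODEL) and in the other models with a random centre effect in 7.1.3 and 7.2.2. State a fallback if a Tier has too few centres.
2. **Degrees of freedom.** State that the primary treatment test and interval use between-centre df = centres − 3 = 9. Prespecify a Tier-adjusted centre-level t analysis on 9 df as a check.
3. **Power.** Restate Protocol 9.2.1 and Table 2 in 9.2.2 on that basis, and say whether ICC 0.01 is within Tier or total.
4. **Consistency.** Align Protocol 9.4 and 9.4.1, and record the change in SAP 2.1, which now reports no changes to the planned analysis.

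No new data are needed, since Tier is known at randomisation. The edits reach the protocol as well as the SAP. The critical value rises by 15% (2.262 against 1.960). The interval is about 15% wider if Tier has no effect, about 2% wider at a 10-point gap and about 9% narrower at 15 points. The stated power becomes less favourable. Adding centres is not required; the lower power can be stated as a limitation.

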4.3. Type and Number of Subjects

A total of 528 subjects are required including a total of 12 centres (6 centres per group) and around 44 asthma subjects per centre.

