9.2. Sample Size Considerations

9.2.1. Sample Size Assumptions

The study will be powered to demonstrate superiority of ACT guided treatment over usual care from baseline over Week 24 in the primary endpoints.

We assume an intra-cluster correlation coefficient (ICC) of $\rho=0.01$, 29% well-control rate for usual care group, and 44% for ACT guided treatment group. It is required to have 6 centres for each treatment group and a minimum of 35 subjects for each centre (a total of 420 evaluable subjects) to achieve a power of 80% with two-sided $\alpha=0.05$. We anticipate a dropout rate of 20% and therefore planned to recruit 44 subjects in each centre (a total of 528 randomized subjects). These sample size calculations are produced based on Donner [[Donner, 1981](#)].

An ACT score ≥ 20 indicates controlled asthma. The assumed rate of subjects with an ACT score ≥ 20 for usual care group is based on a nationwide epidemiologic survey in

China [Nan, 2013], which reported a 29% asthma control rate. The rate for ACT guided treatment is assumed based on GOAL study [Bateman, 2004], which reported a 80% rate for salmeterol/fluticasone group. An additional adjustment has been made to reduce it to 44% to account for real life practice. A 15% difference between ACT guided treatment group and usual care group is considered clinically meaningful.

Study centres will be randomly assigned to the 2 groups using a computer generated randomization list. The randomization will be stratified according to the Tier of the hospitals (Tier 3 vs. Tier 2).

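### The planned treatment-by-centre interaction test cannot be carried out as an interaction test, because every centre is randomised whole to a single arm

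*SAP*

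**What the plan says.** SAP 5.3 sets the design: "each study centre, considered as a cluster, will be randomized to either ACT guided treatment group or control group (usual care group". Protocol 4.3 gives the numbers: "A total of 528 subjects are required including a total of 12 centres (6 centres per group". Protocol 4.4 explains that whole centres are randomised to avoid contamination from one investigator looking after subjects in both groups.

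The primary analysis (SAP 7.1.2) is a mixed-effects logistic regression. Centre enters the example code only through "random intercept/subject= invsite" and does not appear in the MODEL statement.

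The same section then plans the interaction work: "Interactions between treatment and each of the covariates will be investigated in turn, with all main effects in the model". It continues: "Any interaction terms found to be statistically significant will be explored and if necessary results will be reported for each level of the covariate". The level is set in the last sentence: "The effect of interactions (e.g., treatment by centre) will be assessed at the 10% level of significance". Protocol 9.4.3 says the same. Treatment by centre is the only interaction that either document names, and neither gives code for it.

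**The concern.** A treatment-by-centre interaction asks whether the difference between arms varies from centre to centre. To answer it, at least some centres must treat subjects in both arms. Here none does, by design. Six centres supply only ACT guided subjects and six supply only usual care subjects, so there is no within-centre difference to compare.

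What is at stake is how the output would be read. The analyst will get one of two things, depending on how the term is coded. One is no test, which could be written up as no evidence of interaction. The other is a p-value that carries an interaction label but measures something else, and a small one would set off the plan's own instruction to explore and report by level. Neither bears on whether the effect is consistent across centres.

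**Working it through.** **Inputs.** 12 centres, 6 per arm (Protocol 4.3). At least 35 evaluable subjects per centre, intra-cluster correlation (ICC) 0.01 and 20% dropout (Protocol 9.2.1). Response rates from the same section: "29% well-control rate for usual care group, and 44% for ACT guided treatment group". Interaction level 10% (SAP 7.1.2). The documents give no degrees of freedom for any interaction test.

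**1. The plan's own sample size, to confirm the inputs.**
- Per arm without clustering (pooled variance, two-sided 0.05, 80% power, mean rate 0.365): n = [1.96·√(2·0.365·0.635) + 0.84·√(0.29·0.71 + 0.44·0.56)]² / 0.15² ≈ 161.
- Design effect: 1 + (35 − 1)·0.01 = 1.34.
- Per arm with clustering: 161 × 1.34 = 215.7, against 6 × 35 = 210 planned. The unpooled variant gives 157.8 × 1.34 = 211.4.
- Power at 210 per arm (effective 210/1.34 = 156.7) is 79.0%, against 80% stated.
- Dropout: 35/0.8 = 43.75, rounded to 44 per centre; 44 × 12 = 528.

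The stated figures reproduce closely, so the same inputs are used below.

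**2. Centre as a fixed effect.** For 12 centres nested 6:6 in two arms, the ranks of the design matrix are:

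| Columns | Rank |
|---|---|
| intercept + treatment | 2 |
| intercept + treatment + centre | 12 |
| intercept + treatment + centre + treatment×centre | 12 |

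Interaction df = 12 − 12 = 0. Only 12 of the 24 treatment-by-centre cells contain subjects. Had every centre contained both arms, the df would be 11.

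**3. Centre as a random effect.** A classification-type random treatment×centre effect gives exactly the covariance structure of the random intercept already in the model: subjects in the same centre share one effect, and those in different centres share none. The two variances cannot be separated.

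**4. Product term added to the SAP's example model.** That model has no fixed centre term, so adding treatment×centre to intercept + treatment raises the rank from 2 to 12, which is 10 df. Those 10 df are the differences among 6 centres within one arm (5) plus those among 6 centres within the other (5). They are between-centre variation. The plan already assumes such variation exists, through its non-zero ICC, whether or not the treatment effect varies.

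**5. How often that 10-df test would be significant with no treatment heterogeneity.**
- By simulation: Pearson chi-square on 10 df, rates 29% and 44%, 35 per centre, beta-binomial variation between centres, no covariates, 10% level. It rejects about 29% of the time at ICC 0.01. At assumed ICCs of 0.02 and 0.05 it rejects about 50% and 84%.
- By hand at ICC 0.01: the 10% critical value of chi-square on 10 df is 15.99. Clustering inflates the statistic by about 1.34, so the rejection rate is roughly P(χ²₁₀ > 15.99/1.34 = 11.93) = 0.29, in agreement.

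**6. The other planned interactions.** Treatment with baseline ACT, baseline ACT squared, baseline controller, gender and age each keep 1 df and can be estimated.

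**The case against.** The best defence is that this is one parenthetical example in an exploratory paragraph. Protocol 9.4.3 files it under other analyses. The SAP's variable list names centre as the random effect, separately from the covariates, so the rule about testing each covariate need not reach it. The listed subgroups (SAP 5.4 and 7.1.3) are controller, gender and age, and no by-centre effect analysis is described. All of this is fair and limits the importance of the point. It does not remove it: both documents name treatment by centre outright as an interaction to be assessed at 10%.

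A reader might infer more than the documents support:

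- **That the analysis must fail or return a missing test.** The 0 df in step 2 assumes a fixed centre effect, which the SAP does not specify. With the SAP's model, a printed 10-df test is a plausible result.
- **That any random treatment slope by centre is confounded with the intercept.** This is not so in general. With 0/1 treatment coding, an independent slope amounts to a different between-centre variance in each arm, which is a distinct structure. It is still not a within-centre treatment effect, and the SAP specifies no such term.
- **That no by-centre results can exist.** By-centre treatment effects cannot, but by-centre response rates can.
- **That testing several covariate interactions at 10% is part of this fault.** Those tests are estimable, and a 10% screening level for exploratory work is a choice rather than an error.

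**Conclusion.** The point stands, with limited scope. As written, both documents pre-specify a test that the cluster design cannot deliver: it is either empty (0 df with centre fixed) or a mislabelled 10-df test of between-centre variation.

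That the interaction cannot be estimated follows from the design alone, and recruiting more subjects under the same allocation would not change it. The 29% is approximate. It rests on the plan's ICC of 0.01, 35 subjects in each centre, the assumed response rates, beta-binomial variation and a test without covariates. It rises quickly if the true ICC is larger. Which of the two outputs would appear depends on coding that the documents do not give.

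It would be wrong to conclude that the primary result is compromised. The treatment comparison with centre as a random intercept, the sample size and the other covariate interactions do not depend on this test.

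**What to change.** In SAP 7.1.2 and Protocol 9.4.3, delete the parenthetical that names treatment by centre, and state that centre is excluded from the interaction tests because each centre has one arm. In its place, report the estimated between-centre variance (or ICC) from the primary model, and list the centre response rates by arm as description only.

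Optionally, add an exploratory treatment-by-Tier interaction. Hospital Tier is the randomisation stratum, and it is a centre-level heterogeneity question that the design can address, provided both Tiers occur in both arms. The documents do not give the Tier split, so this has to be confirmed first. It should be judged on between-centre degrees of freedom: 12 centres − 4 Tier-by-arm cells = 8 if all four cells are filled. Its power would be low, and the SAP should say so.

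The cost is a wording change in two documents, one descriptive display and at most one extra model term. No change to data collection or to the primary analysis is needed.
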